5. SAFETY AND ADVERSE EVENTS

5.1. Adverse Events

An adverse event (AE) is any untoward medical occurrence associated with the use of a drug in humans, whether or not considered drug related.

- Solicited AEs (i.e., reactogenicity parameters as defined in [4.3.6](#)) will be recorded without attribution assessments by the subject on paper or electronic diary for 7 days after each product administration.
- Unsolicited AEs will be recorded in the study database with attribution assessments from product administration through the Day 28 post-product administration visit.
- SAEs (as detailed in [5.2](#)) and new chronic medical conditions will be recorded as AEs through the last expected study visit or contact.

[Appendix II](#) describes how the relationship between an AE and the study product will be assessed. Also available in [Appendix II](#) is the link to the DAIDS Table for Grading the Severity of Adult and Pediatric Adverse Events, Corrected Version 2.1 [July 2017], which will be used to determine the severity grades of AEs in this protocol with several modifications as noted.

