4.3.9. Concomitant Medications

Only routine prescription medications will be entered in the database at the time of enrollment. Subsequently, concomitant medications are only updated or recorded in the study database if there is an occurrence of an adverse event (AE) that requires expedited reporting, a change to pre-existing condition treatment, or the development of a new chronic condition that requires ongoing medical management. Receipt of an FDA-approved vaccine at any time during the study will be recorded in the database. Clinicians should work with subjects regarding the timing of licensed vaccines relative to study product administration as indicated in [4.3.4](#). Otherwise, concomitant medication changes throughout the study will be recorded in the subject’s chart as needed for general medical documentation but will not be recorded in the database.

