4.6. Criteria for Discontinuation of VRC01.23LS Administration

Under certain circumstances, a subject may be prohibited from receiving further study product administrations. These include:

- Grade 3 adverse event assessed as related to VRC01.23LS (with the exception of self-limited Grade 3 solicited reactogenicity that resolve during the solicited reactogenicity period);
- Grade 4 adverse event assessed as related to VRC01.23LS;
- SAE assessed as related to VRC01.23LS;
- Immediate hypersensitivity reaction associated with VRC01.23LS;
- Intercurrent illness that is not expected to resolve prior to the next scheduled study product administration and for which PI (or designee) believes is in the best interest of the subject to restrict further exposure;
- Repeated failure to comply with protocol requirements.

Subjects who receive at least one dose of VRC01.23LS but are discontinued from further study product administrations will continue with follow-up as shown in the Schedule 5 of the Schedule of Evaluations with the exception that research sample collections will be discontinued for pregnant women or others in which it is contraindicated.

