4.7. Criteria for Pausing and Resuming the Study

The study team will closely monitor and review study data as they become available to make determinations regarding the presence and severity of adverse events (AEs). Study product administrations and new enrollments will be paused if any of the following criteria are met:

- **One** (or more) subject experiences a serious adverse event (SAE) that is assessed as related (possible, probably, or definitely) to the study product, or
- **Two** (or more) subjects experience the same **Grade 3 or higher AE** that is assessed as related (possible, probably, or definitely) to study agent (other than self-limited Grade 3 AEs that resolve during the solicited reactogenicity period).

In the event of a pause, the IND Sponsor Medical Officer (MO) and the PSRT will be promptly notified.

Plan for Review of Pauses and Resuming Rules:

Study product administration and enrollments would resume only if review of the AEs that caused the pause results in a recommendation to permit further study product administrations and study enrollments. The reviews to make this decision will occur as follows:

- **Pauses for related SAEs:** The IND Sponsor Medical Officer (MO), with participation by the PI, will conduct the review and make the decision to resume, amend or close the study. The IRB and FDA will be notified accordingly.
- **Pauses for Grade 3 or higher related AEs:** The IND Sponsor MO, in consultation with the PI, will conduct the review and make the decision to resume, amend or close

the study for the Grade 3 or higher AEs that meet criteria for pausing the study. As part of the pause review, the reviewers will also advise on whether the study needs to be paused again for any subsequent events of the same type. The FDA and the IRB will be notified of Grade 3 or higher pause reviews and of the IND Sponsor's decisions.

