5.2. Serious Adverse Events

The term "Serious Adverse Event" (SAE) is defined in 21 CFR 312.32 as follows: "An adverse event or suspected adverse reaction is considered serious if, in the view of either the investigator or the sponsor, it results in any of the following outcomes: Death, a life-threatening adverse event, inpatient hospitalization or prolongation of existing hospitalization, a persistent or significant incapacity or substantial disruption of the ability to conduct normal life functions, or a congenital anomaly/birth defect. Important medical events that may not result in death, be life-threatening, or require hospitalization may be considered serious when, based upon appropriate medical judgment, they may jeopardize the patient or subject and may require medical or surgical intervention to prevent one of the outcomes listed in this definition. Examples of such medical events include allergic bronchospasm requiring intensive treatment in an emergency room or at home, blood dyscrasias or convulsions that do not result in inpatient hospitalization, or the development of drug dependency or drug abuse."

Life-threatening adverse event or life-threatening suspected adverse reaction. An adverse event or suspected adverse reaction is considered "life-threatening" if, in the view of either the investigator or sponsor, its occurrence places the patient or subject at immediate risk of death. It does not include an adverse event or suspected adverse reaction that, had it occurred in a more severe form, might have caused death. "Life-threatening" refers to an AE that at occurrence represents an immediate risk of death to a subject. It does not include an adverse event or suspected adverse reaction that, had it occurred in a more severe form, might have caused death. Similarly, a hospital admission for an elective procedure is not considered a SAE.

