9.3.2. Data Collection

Clinical research data will be collected in a secure electronic web-based clinical data management system (CDMS) through a contract research organization, The Emmes Company LLC (Rockville, MD). Extracted, anonymized data will be sent to the PSRT for safety review and to Protocol Statistician for statistical analysis.

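### Section 5.1 does not require acute, non-serious Grade 3+ AEs arising after the Day 28 post-dose visit to be recorded and attributed, although Groups 5 and 6 are dosed again about 56 days later (minor)

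*Combined protocol and SAP*

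**What the plan says.** Section 5.1 sets the recording rule: "Unsolicited AEs will be recorded in the study database with attribution assessments from product administration through the Day 28 post-product administration visit". Beyond that visit it keeps two categories open, SAEs and new chronic conditions: "new chronic medical conditions will be recorded as AEs through the last expected study visit or contact". It makes no separate provision for severe but non-serious events.

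Groups 5 and 6 receive doses at Day 0, Week 12 and Week 24 (section 1.4, Table 2). Section 4.6 lists among the reasons to withhold further doses a "Grade 3 adverse event assessed as related to VRC01.23LS", apart from self-limited solicited reactions, and any related Grade 4 event. Section 4.7 pauses the study when two subjects have the same Grade 3 or higher AE "assessed as related (possible, probably, or definitely) to study agent", with a similar exception. Neither rule has a time limit, and neither is confined to events entered in the database.

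Section 6.3.3 summarizes unsolicited AEs by group and lists laboratory data by subject over the whole study.

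**The concern.** The rules that protect a subject before a repeat dose depend on a related Grade 3 or higher event, and so on someone judging relatedness. The text that requires that judgement to be entered in the database lapses at the Day 28 visit, well before the next dose. A severe neutropenia or transaminase rise, or a short severe illness, that is neither serious nor chronic could arise and resolve in that interval without becoming an attributed AE.

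What is at stake is the completeness of the AE record in a first-in-human study whose primary objectives include the safety of each repeat-dose regimen (section 3.1). An event that 5.1 does not make recordable can be absent from the by-group tables. A laboratory value would remain in a listing without attribution. A clinical event might appear in no planned output.

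**Working it through.** The plan gives no figure for this interval, so it is derived from the schedules. The event probabilities in 6.2.2 are a separate matter. They reproduce (for n=5, 1 − 0.1^(1/5) = 0.369) and are framed around SAEs, which 5.1 records to the last visit.

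**Length of the interval, Groups 5 and 6**

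- Inputs: doses at Days 0, 84 and 168; Day 28 post-dose visits at Day 28 (Visit 06) and Day 112 (Visit 11); windows of ±7 days on Visits 06, 08, 11 and 13 (Appendix I, Schedules 3 and 4).
- Nominal: 84 − 28 = 56 days, and again 168 − 112 = 56 days. Strictly this is 55 full days (Days 29 to 83) plus the pre-dose part of the dosing day.
- Shortest: (84 − 7) − (28 + 7) = 77 − 35 = 42 days.
- Longest: (84 + 7) − (28 − 7) = 91 − 21 = 70 days.
- Before the third dose: 2 × 56 = 112 of 168 days, or 67%.

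**Opportunities to detect an event in the interval**

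- Scheduled clinic visits: Weeks 8, 12 (pre-dose), 20 and 24 (pre-dose). At target enrolment, 4 × 10 subjects = 40 visits.
- Safety labs (CBC 3 mL, ALT/creatinine 4 mL) can be identified from the daily volumes. A 19 mL visit is PK 4 + serum 8 + labs 7, a 22 mL visit adds the 3 mL HIV test, and the 31 mL visit is PK 4 + PBMC 20 + labs 7. A 12 mL visit has no safety labs.
- Cumulative volumes confirm labs at Weeks 12 and 24: Schedule 3 rises from 192 to 211 and from 302 to 321; Schedule 4 from 196 to 215 and from 314 to 333. Each step is 19 mL. Weeks 8 and 20 add 12 mL, so they have no safety labs.
- Draws per subject after the first dose: 4 in the 28 days after dose 1, 1 before dose 2, 4 after dose 2, 1 before dose 3 and 4 after dose 3, giving 14. Two fall outside required recording.
- Total: 10 × 14 = 140 draws, of which 10 × 2 = 20 (14%) are outside. These 20 are the only scheduled safety labs between the Day 28 visit and the next dose.

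**What happens to a pre-dose abnormality**

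Labs are repeated at 72 hours in Group 5 (Visits 08G, 13G) and 48 hours in Group 6 (Visits 08F, 13F), then 1, 2 and 4 weeks after the dose. All of these fall in the next recording window. Day 0 remains the baseline for AEs (Appendix I, footnote 1), so the pre-dose value does not reset it. An abnormality that persists is therefore recordable with attribution, though only after the next dose has been given. One that clears within days is not.

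**Context only: exposure**

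Section 1.1 expects a half-life comparable to 71 ± 18 days. Assuming terminal-phase decline, the Day 84 to Day 28 concentration ratio is 2^(−56/71) = 0.58, with 0.48 at 53 days and 0.65 at 89 days. Drug is still present through the interval. This says nothing about event risk.

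**The case against.** The 28-day window is a stated design choice that no other section contradicts, and it leaves out a narrow class of event. The documents expect mainly early reactions (sections 1.3.2 and 8.2.1) and give no rate for late ones.

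A reader might infer that the stopping and pause rules cease to work after Day 28. The documents do not support that. Section 4.7 has the study team "closely monitor and review study data as they become available to make determinations regarding the presence and severity of adverse events"; 4.3.6 has clinicians assess symptoms throughout; and Appendix II has the investigator judge relatedness without a time limit. The SAE definition in 5.2 reaches important medical events, with examples such as "blood dyscrasias or convulsions that do not result in inpatient hospitalization". Section 5.5.1 requires an unanticipated problem to be reported to the IRB within 7 calendar days, with no Day 28 limit and no seriousness criterion. Section 4.6 also allows doses to be withheld for an unresolved intercurrent illness.

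A reader might also infer that the safety review team (PSRT) would not learn of an unentered event, because 9.3.2 says: "Extracted, anonymized data will be sent to the PSRT for safety review and to Protocol Statistician for statistical analysis". But 8.9 puts the site's own investigators and study clinicians on that team at a single site, so they may know of the event directly. Section 8.9 also provides a daily safety review under procedures that are not in the documents, so what those procedures require is unknown.

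Nor does the gap explain why medication changes stay in the chart and "as needed for general medical documentation but will not be recorded in the database". Section 4.3.9 applies that rule throughout the study, including inside the 28-day window.

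These objections stand, and they make the point minor. They do not remove it. None of these routes requires entry and attribution of every such event as an AE, least of all one that has already resolved. IRB reporting does not populate the AE tables.

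**Conclusion.** The point holds as a minor gap in the AE record. As written, 5.1 does not require an acute, non-serious, non-chronic Grade 3 or higher event to be recorded and attributed if it arises in the nominal 56 days (42 to 70) between the Day 28 visit and the next dose in Groups 5 and 6. Such an event could be absent from the by-group summaries.

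The effect on subject protection is small, since the rules in 4.6 and 4.7 still operate. The effect on laboratory findings is smaller still: values are listed, and persistent abnormalities enter the next window. The 40 visits and 20 draws count opportunities to detect an event, not events lost. The conclusion rests on a literal reading of 5.1, on target enrolment of 10 subjects in Groups 5 and 6, and on the supplied documents alone.

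**What to change.** Amend 5.1 so that Grade 3 or higher AEs, including graded laboratory abnormalities, found at already scheduled visits between the Day 28 visit and the next dose in Groups 5 and 6 are recorded with investigator attribution. In 6.3.3, tabulate them separately so that the planned 28-day summary is unchanged.

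Dosing-day laboratory results may return after that dose is given, so recording them would mainly inform the pause rule and later doses.

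The cost is one or two sentences, a few extra AE entries and slightly higher AE counts. No visits, blood draws, pause thresholds or dosing rules change.

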5.2. Serious Adverse Events

The term "Serious Adverse Event" (SAE) is defined in 21 CFR 312.32 as follows: "An adverse event or suspected adverse reaction is considered serious if, in the view of either the investigator or the sponsor, it results in any of the following outcomes: Death, a life-threatening adverse event, inpatient hospitalization or prolongation of existing hospitalization, a persistent or significant incapacity or substantial disruption of the ability to conduct normal life functions, or a congenital anomaly/birth defect. Important medical events that may not result in death, be life-threatening, or require hospitalization may be considered serious when, based upon appropriate medical judgment, they may jeopardize the patient or subject and may require medical or surgical intervention to prevent one of the outcomes listed in this definition. Examples of such medical events include allergic bronchospasm requiring intensive treatment in an emergency room or at home, blood dyscrasias or convulsions that do not result in inpatient hospitalization, or the development of drug dependency or drug abuse."

Life-threatening adverse event or life-threatening suspected adverse reaction. An adverse event or suspected adverse reaction is considered "life-threatening" if, in the view of either the investigator or sponsor, its occurrence places the patient or subject at immediate risk of death. It does not include an adverse event or suspected adverse reaction that, had it occurred in a more severe form, might have caused death. "Life-threatening" refers to an AE that at occurrence represents an immediate risk of death to a subject. It does not include an adverse event or suspected adverse reaction that, had it occurred in a more severe form, might have caused death. Similarly, a hospital admission for an elective procedure is not considered a SAE.

5.3. Adverse Event Reporting to the IND Sponsor

AEs that meet SAE criteria must be reported and submitted by the clinical site on an expedited basis to the IND Sponsor, VRC/NIAID/NIH, according to Sponsor guidelines as follows:

- Results in death
- Is life threatening
- Results in persistent or significant disability/incapacity
- Requires unplanned inpatient hospitalization or prolongation of existing hospitalization
- Is a congenital anomaly/birth defect in the offspring of a study subject
- Is an important medical event that may jeopardize the subject or may require intervention to prevent one of the other outcomes listed above.

In addition, any event, regardless of severity, which in the judgment of an investigator represents a SAE, may be reported on an expedited basis.

An investigator will communicate an initial SAE report within 24 hours of site awareness of occurrence to the IND Sponsor by data entry into the database, which triggers an alert to the IND Sponsor MO. Within 3 working days, a written summary by the investigator should be submitted to the IND Sponsor.

In order for the IND Sponsor to comply with regulations mandating sponsor notification of specified SAEs to the FDA within 7 and/or 15 calendar days, the investigator must submit additional information as soon as it is available.

5.4. IND Sponsor Reporting to the FDA

The IND Sponsor is responsible for making the determination of which SAEs are “serious and unexpected suspected adverse reactions” (SUSARs) as defined in 21 CFR 312.32.

- *Suspected adverse reaction* means any adverse event for which there is a reasonable possibility that the drug caused the adverse event.
- *Unexpected Adverse Event* means an AE that is not listed in the IB or is not listed at the specificity or severity that has been observed.

All SUSARs (as determined by the IND Sponsor) will be reported to the FDA as IND Safety Reports; IND Safety Reports will also be provided to the IRB.

The IND Sponsor will also submit an IND Annual Report of the progress of the investigation to the FDA as defined in 21 CFR 312.32.

5.5. Reporting to the Institutional Review Board

The following information is consistent with NIH IRB Policy 801: Reporting Research Events.

Reportable Event - An event that occurs during the course of human subject research that requires notification to the IRB.

For the purposes of this policy, reportable events include the following:

- Unanticipated Problems (UPs) involving risks to subjects or others,

- Non-compliance (including major protocol deviations and noncompliance that is not related to a protocol deviation),
- Deaths related or possibly related to research activities, and
- New information that might affect the willingness of subjects to enroll or continue participation in the study.

5.5.1. Unanticipated Problem (UP) Definition

An unanticipated problem (UP) is defined as any incident, experience, or outcome that meets **all** of the following criteria:

- Unexpected (in terms of nature, severity, or frequency) given (a) the research procedures that are described in the protocol-related documents, such as the IRB-approved research protocol and informed consent document; and (b) the characteristics of the subject population being studied; **and**
- Related or possibly related to participation in the research (possibly related means there is a reasonable possibility that the incident, experience, or outcome may have been caused by the procedures involved in the research); **and**
- Suggests that the research places subjects or others (which may include research staff, family members or other individuals not directly participating in the research) at a greater risk of harm (including physical, psychological, economic, or social harm) related to the research than was previously known or expected.

A UP must be reported within 7 calendar days of an investigator becoming aware of the actual or suspected UP.

5.5.2. Non-Compliance Definition

Non-compliance is the failure of investigator(s) to follow the applicable laws, regulations, or institutional policies governing the protection of human subjects in research, or the requirements or determinations of the IRB, whether intentional or not.

Non-compliance may be unintentional (e.g. due to lack of understanding, knowledge, or commitment), or intentional (e.g. due to deliberate choice to ignore or compromise the requirements of any applicable regulation, organizational policy, or determination of the IRB).

Non-compliance is further characterized as serious or continuing as follows:

- Serious non-compliance - Non-compliance, whether intentional or not, that results in harm or otherwise materially compromises the rights, welfare and/or safety of the subject. Non-compliance that materially affects the scientific integrity or validity of the research may be considered serious non-compliance, even if it does not result in direct harm to research subjects.
- Continuing non-compliance- A pattern of recurring non-compliance that either has resulted, or, if continued, may result in harm to subjects or otherwise materially compromise the rights, welfare and/or safety of subjects, affect the scientific integrity

of the study or validity of the results. The pattern may comprise repetition of the same non-compliant action(s), or different noncompliant events.

Any actual or suspected non-compliance by any investigator or entity associated with the protocol must be reported to the IRB by the PI/designee within 7 calendar days of any investigator or individual associated with the protocol first becoming aware.

5.5.3. Protocol Deviation Definition

A protocol deviation is defined as any change, divergence, or departure from the IRB-approved research protocol and is further characterized as major and minor as follows:

- Major Deviations – Deviations from the IRB approved protocol that have, or may have the potential to, negatively impact, the rights, welfare or safety of the subject, or to substantially negatively impact the scientific integrity or validity of the study.
- Minor Deviations – Deviations that do not have the potential to negatively impact the rights, safety, or welfare of subjects or others, or the scientific integrity or validity of the study.

For the reporting purposes, failure of subjects to comply with the research protocol does not represent non-compliance unless that failure is due to an action or omission of a member of the research team, for example, the failure to give adequate instruction to the subject.

A major deviation must be reported within 7 calendar days of an investigator becoming aware of an actual or suspected deviation. Although PDs are also non-compliance, these should only be reported once as deviations. Major deviations resulting in death must be reported within 24 hours of the occurrence of the event or of any member of the study team becoming aware of the death.

Researchers are responsible for monitoring their studies throughout the year for adherence to the IRB-approved protocol. The purpose of this monitoring is to identify major deviations and to look for trends in minor deviations that may indicate a systemic issue in how the study is being conducted that could potentially negatively impact the rights, safety, or welfare of participants or the study's ability to produce scientifically valid results. A series of minor deviations pointing toward a more global issue that could affect the rights, safety or welfare of the participant or affect the validity of the study should be reported as a major deviation. In all other instances, a summary of minor deviations should be provided to the IRB at the time of continuing review.

